#### **10.7 Power for analysis of critical secondary variables**

Correlation between laboratories will be checked periodically throughout the study period. eGFR will be calculated using MDRD formula for each visit following the kidney transplantation. All data will be analyzed using the intent-to-treat approach as well as on-treatment based approach. Comparisons between treatment groups experiencing composite efficacy failure and each component will be analyzed with Fisher's exact test. The Chi-square and/or one-way analysis of variance (ANOVA) will be used for acute rejection episodes and creatinine levels respectively.

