#### **4 Study Design**

This is a 24 month, Single Center, Open-Label, Randomized, Parallel assignment, non-inferiority pilot study of safety and efficacy, comparing Everolimus with low-dose Tacrolimus (2 arms; 1 arm will involve a conversion to MMF/MPA at month 3) and the standard of care (with standard dose Tacrolimus and MMF/MPA) in recipients of DCD and elevated KDPI kidneys. For this study, either MMF 1,000 mg BID or MPA 720 mg BID will be allowed since MMF and MPA are considered to be therapeutically equivalent.

All study patients must give a signed informed consent voluntarily prior to any study-related activities. Once a signed consent is obtained, baseline assessment including laboratory testing will take place to determine patient's eligibility to participate in the study. Baseline assessments will occur in the time period starting 3 weeks pre-transplantation and ending at the time of transplantation. Eligible patients will receive Campath or Simulect as an induction therapy according to the institutional practice.

Randomization will occur within 24-hour of transplantation. Fifty patients who meet the inclusion/exclusion criteria will be randomized to receive their first dose of study drug (0.75 mg Everolimus (2 arms) or 1,000/720 mg MMF/MPA) within 24 hours of transplantation (Figure 4-1). The first dose of Tacrolimus will be given to all study participants according to our standard practice. Patients will be assigned to either continuation on low-dose Tacrolimus (Arm 1), to conversion from low-dose Tacrolimus to Mycophenolate at month 3 (Arm 2), or to standard therapy with Tacrolimus and Mycophenolate (Arm 3).

Everolimus and Tacrolimus levels will be monitored throughout the study, and respective doses will be adjusted according to the desired trough levels. Patients will be started on 0.75mg BID. Everolimus will be dosed to target trough levels of 3 to 8 ng/ml, starting on Day 7.

Earlier increase in Everolimus level may decrease Tacrolimus exposure, which may lead to under-immunosuppression; increasing the risk of acute rejection (16). Therefore, Day 7 $\pm$ 1 was chosen to initiate the first dose adjustment for Everolimus after careful consideration of the half-life of this drug and turnaround time of the trough level availability. The target Everolimus trough level was determined based on the Novartis B201 and B251 studies (17).

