## **On Day 7 after initiation of Everolimus treatment**

For Arm 1 and Arm 2 (ERL groups), the 0.75 mg BID dose will be increased if the ERL trough level is < 3 ng/mL, and reduced if the ERL trough level is > 8 ng/mL until Month 3. Starting at Month 3, ERL will be dosed to target levels of 5 to 8 ng/mL. The dose will be increased if the ERL trough level is < 5 ng/mL, and reduced if the ERL trough level is > 8 ng/mL.

Everolimus dose adjustments should be made on results of the trough levels from the hospital laboratory. Tacrolimus dose adjustments should be made based on the results of the trough levels done at the local laboratory. Tacrolimus trough levels will also be run at the hospital laboratory for purposes of the protocol.

Follow-up ERL and TAC trough levels should be measured 5-7 days after any dose adjustment to ERL or TAC to ensure that the recommended troughs are achieved.

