#### **6.5.7.2 Initiation and maintenance of Tacrolimus**

It is recommended that the initial dose of TAC be administered according to our standard of care practice within 24 hours after reperfusion of the graft. If patients experience DGF, TAC can be held for up to and including 14 days. However, TAC or study medication (ERL or MMF/MPA) must be started within 24 hours post-transplant. Subsequently, ERL dosing will be adjusted according to trough level results from the reference laboratory. Tacrolimus whole-blood trough concentrations will be determined on all study visits. Target TAC trough levels will be as follows in Table 6-1. Target therapeutic ranges for TAC C0-h levels in whole blood will be assessed at the hospital laboratory for purposes of this protocol.

If, for any time throughout the study, TAC is held for > 14 days, ERL should be discontinued and the patient discontinued from the study. These patients should be followed throughout the remainder of the study to Month 24 on a follow-up schedule. See Section 7.5, Safety assessments, Follow-up of prematurely discontinued patients.

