## **7.3 Treatment exposure and compliance**

All doses of study medication administered during the course of the study will be recorded on the appropriate Study Drug Dosage Administration CRF. Everolimus trough levels will be determined by the designated hospital laboratory.

Tacrolimus dosing will be entered on a separate TAC Dosage Administration CRF. Tacrolimus trough levels will be locally determined and recorded on the relevant CRF. Dose adjustments will be made based on local assay results.

Immunosuppressive therapies will be recorded on a separate Immunosuppressive Therapies CRF. Steroids will be recorded until steroid withdrawal occurs in accordance with MGTI's standard practice.

For all immunosuppressants, the start date, total dose, stop date and reason for administration or change are to be provided. If study drug is interrupted due to inability to tolerate oral medication and rescue therapy via an NG tube is administered the non-study drug immunosuppressive (i.e. crushed ERL suspension) should be recorded on the Immunosuppressive medications CRF. For anti-hypertensive medications,

Other drugs administered prior to and continuing at start of study medication will be entered on the 'Concomitant medications' CRF.

Immunosuppressive drugs administered prior to and continuing at start of study medication will be entered on the 'Immunosuppressive Medications' CRF.

Compliance will be assessed by the investigator and/or study personnel using pill counts (will be obtained from Investigational Drug Service pharmacy) and information provided by the patient. This information should be captured in the source document.

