### **7.5.6 Laboratory evaluations**

All laboratory tests will be done at the hospital affiliated laboratory. Laboratory samples should be drawn prior to administration of the morning dose of both TAC and study medication. All samples will be drawn with the patient in the fasting state (more than eight hours after the last meal) if possible. Non-fasting blood samples will be clearly identified.

Therapeutic drug monitoring (TDM) will be mandatory throughout the study. The transplant team will be alerted when ERL trough levels are < 3 ng/mL or > 8 ng/mL to adjust the dose of ERL. All ERL dose adjustments will be made based on these results.

Blood samples for TAC trough levels from the hospital affiliated laboratory will be used to obtain tacrolimus trough levels. Adjustments should be made for TAC using the trough levels from the laboratory.

Extreme values will be reported to the investigator and/or the study team for immediate action as per standard of care. The Investigator is asked to comment on these abnormalities if they are clinically significant in the CRF.

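### The only between-laboratory check is a correlation, which in its ordinary form cannot show a constant or proportional bias in tacrolimus troughs

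*Combined protocol and SAP*

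**What the plan says.** Section 10.7, under a heading about power for secondary variables, contains one sentence on comparability: "Correlation between laboratories will be checked periodically throughout the study period". It gives no type of coefficient, analyte, number of paired samples, acceptance limit or consequence. Nothing elsewhere in the document mentions bias, agreement limits or split samples.

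Two laboratories are named for tacrolimus. Section 6.5.5 (the part on Day 7) says "Tacrolimus dose adjustments should be made based on the results of the trough levels done at the local laboratory" and then "Tacrolimus trough levels will also be run at the hospital laboratory for purposes of the protocol". Section 7.3 agrees on the dosing side: "Tacrolimus trough levels will be locally determined and recorded on the relevant CRF", with dose changes following the local assay. Section 6.5.7.2 has attainment of the tacrolimus target ranges judged at the hospital laboratory.

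Other text points to a single laboratory. Section 7.5.6 says "All laboratory tests will be done at the hospital affiliated laboratory" and takes the tacrolimus troughs used for adjustment from there. Section 4 describes a single-center trial.

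The naming for everolimus also varies. Section 6.5.7.2 says "Subsequently, ERL dosing will be adjusted according to trough level results from the reference laboratory", while Section 7.3 says "Everolimus trough levels will be determined by the designated hospital laboratory"; Sections 6.5.5 and 7.5.6 likewise point to the hospital laboratory.

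The tacrolimus bands in Section 6.5.5 and Table 6-1 are absolute: 4-7 then 2-5 ng/mL in Arm 1, 4-7 ng/mL until conversion in Arm 2, and 8-12 then 6-8 ng/mL in Arm 3.

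**The concern.** Correlation asks whether two laboratories order and space samples alike. The trial needs to know whether they return the same number, because a trough is judged against fixed limits in ng/mL. A laboratory that reads uniformly high, by an amount or by a percentage, correlates just as well as one that reads true.

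On the two-laboratory text, a patient can be dosed into the band on one set of results and lie outside it on the set used to judge target attainment. The contrast between low-dose and standard-dose tacrolimus is part of what the arms are. A report of how well the bands were achieved would then depend on which laboratory's values were used, and the one planned check would give no warning.

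**Working it through.** The plan gives no correlation value, threshold or sample count, so there is no figure of its own to reproduce. The check is whether the stated method can see a bias, and what a bias would do to the bands.

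**Inputs**
- From the documents: tacrolimus band 4-7 ng/mL (Section 6.5.5, Table 6-1), and two named laboratories for tacrolimus (Section 6.5.5).
- Assumed, because the documents give none: size of bias, spread of troughs, assay noise.

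**Step 1: invariance (no assumption needed).** Pearson r = cov(x, y) / (SDx × SDy). Replace y by a + b·y with b > 0. The covariance becomes b·cov(x, y) and the SD of y becomes b·SDy, so b cancels and a drops out: r is unchanged. Spearman's coefficient uses ranks, which this change leaves alone. A numerical check on one simulated set of 16 pairs gave r = 0.9686 with shifts of 0, 1, 2 and 5 ng/mL, and the same with multipliers of 1.2 and 1.5.

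**Step 2: effect on the band (assumed bias, no noise).** Let troughs be uniform on 4-7 ng/mL at one laboratory, so all are in range there.
- Other laboratory reads 20% high: out of range above 7/1.2 = 5.833. Share = (7 - 5.833)/3 = 39%.
- Other laboratory reads 20% low: out of range below 4/0.8 = 5. Share = (5 - 4)/3 = 33%.
- At +10%: 7/1.1 = 6.364, share = (7 - 6.364)/3 = 21%. At -10%: 4/0.9 = 4.444, share = (4.444 - 4)/3 = 15%.
- With no bias the share is 0% by construction.

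**Step 3: the same with assay noise.** Assume normal troughs with mean 5.5 and SD 1.5, and error SD 0.3 at each laboratory. Each laboratory's variance is 2.25 + 0.09 = 2.34 and the covariance is 2.25.
- r = 2.25/2.34 = 0.96 at any constant shift.
- Lin's concordance coefficient is 2·cov / (var1 + var2 + (difference in means)²). With no shift it is 4.5/4.68 = 0.96. With +1 ng/mL it is 4.5/5.68 = 0.79.
- In 400,000 simulated pairs, the share of paired results falling in different categories (below, within, above 4-7) rose from 11% with no shift to 32% at +1 ng/mL. With the SD of troughs between 1 and 2 the ranges were 9-11% and 29-32%.

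So noise alone produces some discordance, a shift of 1 ng/mL roughly triples it, and r does not move.

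**Step 4: could an agreement measure see it?** Assume 6% noise per laboratory and 20 pairs. The SD of a paired percentage difference is about 6% × √2 = 8.5%. The standard error of the mean is 8.5%/√20 = 1.9%, and the 95% half-width is about 1.96 × 1.9% = 3.7%. A bias of 10% would be plain.

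**The case against.** Five objections deserve an answer.

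- **There may be only one laboratory.** At a single center, local and hospital may be the same place, and Section 7.5.6 sends all tests to one laboratory. This stands as a doubt about the facts. It does not rescue the sentence in Section 10.7, which has no purpose if there is one laboratory and the wrong method if there are two.
- **Correlation is undefined.** An intraclass or concordance coefficient would respond to a shift. That is true, and the point is conditional on the ordinary meaning. A reader might infer that a biased laboratory would always pass. The documents do not support that: there is no pass criterion, and imprecision could lower r whatever the bias.
- **eGFR.** A reader might infer that the check also leaves eGFR exposed, since the next sentence in Section 10.7 concerns eGFR. The documents do not support this. Sections 7.5.6 and 7.5.8 assign creatinine to the hospital affiliated laboratory, and no second creatinine laboratory appears.
- **Everolimus.** Only Section 6.5.7.2 speaks of a reference laboratory. That is inconsistent naming; no text says that everolimus is measured twice.
- **Consequence.** Tacrolimus trough is not a primary or secondary variable in Sections 10.4.1 and 10.5.1, and Section 10 plans no trough analysis. This stands, and limits the point to the reading of target attainment.

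**Conclusion.** The point holds for tacrolimus troughs, on two conditions: that correlation means Pearson or Spearman, and that two laboratories really measure tacrolimus, as Section 6.5.5 says. Under those conditions the planned check cannot reveal a constant or proportional bias. The invariance is exact.

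The sizes are illustrations. A bias of 20% either way would move 33% to 39% of in-range troughs out of the 4-7 ng/mL band under a uniform spread without noise. The bias, spread and noise values are assumptions, and the documents do not show that any bias exists.

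No change to the primary composite, to eGFR or to any other secondary endpoint is shown. This is a cheap improvement to the plan, together with a contradiction about laboratories that must be resolved in any case.

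**What to change.** 1. Reconcile Sections 6.5.5, 6.5.7.2, 7.3 and 7.5.6: which laboratory measures tacrolimus and everolimus, which results are used for what, and whose value enters the analysis dataset.
2. If two laboratories measure tacrolimus, replace the sentence in Section 10.7 along these lines: Agreement between the two laboratories will be assessed periodically on paired tacrolimus results, using the mean percentage difference with its 95% CI and Bland-Altman 95% limits of agreement, against a prespecified acceptable bias. If that bias is exceeded, trough summaries will use one named laboratory's values or a documented correction.
3. If only one laboratory is used, delete the sentence. Include everolimus only if a second laboratory is confirmed.

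The cost is wording plus the choice of an acceptable-bias limit. Section 6.5.5 already calls for tacrolimus results at both laboratories, so no new assay should be needed. The document does not say whether both are run on the same draw; if they are not, a modest number of split samples would have to be arranged.

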#### **10.4.1 Variable**

The primary efficacy variable is the composite efficacy failure rate (treated BPAR, graft loss, death or loss to follow-up) at 6, 12 and 24 months post-transplant. The secondary variable is renal function assessed as eGFR during the first 24 months post-transplantation, determined by the MDRD formula. Other secondary variables include the incidences of CMV and BKV, new onset diabetes mellitus, chronic kidney disease with associated proteinuria, adverse events, serious adverse events and tacrolimus associated adverse events.

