#### **10.4.4 Supportive analyses**

Event rates will be compared between treatment groups using the Cochran-Mantel-Haenszel test, stratified by induction therapy.

A logistic regression analysis of the primary efficacy variable will be performed. The odds ratio for treatments, 95% confidence interval for the odds ratio, and p-values (if applicable) will be reported based on the fitted model.

A Kaplan-Meier survival analysis will be performed where all treated BPARs, graft losses, deaths or losses to follow-up that occur up to month 24 will be considered efficacy failures. The incidence of the composite efficacy failure (treated BPAR, graft loss, death or loss to follow-up) within 24 months will be compared between the two treatment groups using Kaplan-Meier probability estimates of efficacy failure and the associated 95% CI obtained

using the standard error derived by applying Greenwood's formula. The differences between the curves will be tested using the log-rank test.

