#### **10.6 Sample size calculation**

Since this is a pilot study, the sample size estimation method proposed by Julious was considered in order to minimize the sample size (14). Julious proposes to employ sample size of 12 per group for a pilot study (14). Assuming the drop out rate of 20% along with the ease of blocked randomization, we propose the sample size of 16 per arm, totaling 48 patients. The estimated effect size,  $\alpha$ , and  $\beta$  corresponding to this sample size are 0.9, 0.05 (two-sided), and 0.2 respectively (15). A block size of 12 along with an allocation ratio of 1:1:1 will be employed as a randomization scheme.

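### Fisher's exact test leaves part of the two-sided 0.05 level unused for the composite failure at 16 per arm; Boschloo's exact test on the same proportions is never less powerful and should be named as the decisive test.

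*Combined protocol and SAP*

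**What the plan says.** Section 10.4.1 defines the endpoint: "The primary efficacy variable is the composite efficacy failure rate (treated BPAR, graft loss, death or loss to follow-up) at 6, 12 and 24 months". Section 10.6 fixes the size: "we propose the sample size of 16 per arm, totaling 48 patients", with alpha 0.05 two-sided.

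Several analyses are attached to this endpoint:

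- Synopsis (Statistical analysis) and section 10.7: "Comparisons between treatment groups experiencing composite efficacy failure and each component will be analyzed with Fisher's exact test". Neither says whether the comparison is pairwise, pooled or across all three arms.
- Section 10.4.2: the analysis labelled primary is an ANOVA on the FAS. No outcome variable is named there.
- Section 10.4.4, as supportive: a Cochran-Mantel-Haenszel test stratified by induction, a logistic regression, and Kaplan-Meier estimates of time to composite failure up to Month 24, for which "The differences between the curves will be tested using the log-rank test". The Kaplan-Meier text speaks of two treatment groups, although the trial has three.
- Section 10.5.1: Kaplan-Meier and log-rank for each component, across three groups.

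No passage gives an expected failure rate, or a size or power for Fisher's test.

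**The concern.** Fisher's test conditions on the total number of failures. In small samples few distinct p-values are then possible, so its true error rate can sit well below the nominal level. The plan allows itself 5%. If the test can spend only 2%, some results that a valid 5% test would call different are called not different. With 16 patients per arm that loss is worth avoiding, because it can be reduced without changing the endpoint, the data or the number of patients.

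The plan also does not say which of its listed tests settles the composite. A better test in section 10.7 would therefore have no defined standing unless section 10.4.2 is changed too.

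**Working it through.** **Inputs.** 16 per arm, 1:1:1, alpha 0.05 two-sided (section 10.6). Loss to follow-up counts as failure (section 10.4.1), so every dosed patient has a Month 24 result and the denominators stay at 16 if all randomised patients are dosed. Failure rates are assumptions.

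**The plan's own figure.** The number per arm follows from the pilot rule: 12 / (1 − 0.20) = 15, raised to 16 so that 48 = 4 blocks of 12. The attached effect size of 0.9 with 80% power does not reproduce two-sided: a t-test at 16 per arm has 69.3% power (normal approximation 72.1%) and would need 20.4, so 21, per arm. One-sided 0.05 gives 80.0%. None of this describes Fisher's test on a proportion.

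**Size of Fisher, 16 v 16.** For a common failure rate p,

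size(p) = Σₐ Σ_b 1[Fisher p(a,b) ≤ 0.05] · Bin(a; 16, p) · Bin(b; 16, p), summed over all 17 × 17 tables.

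**Boschloo.** Use Fisher's two-sided p as the statistic and reject when it is at most c, where c is the largest attainable value whose size, maximised over p, stays within 0.05. Here c = 0.0732. The next attainable value, 0.0756 (11 v 5 failures), would give 5.01%. Because c exceeds 0.05, every table that Fisher rejects is also rejected. The added tables, with their Fisher p-values, are 8 v 2 and 14 v 8 (0.054), 9 v 3 and 13 v 7 (0.066), 10 v 4 and 12 v 6 (0.073), and their mirror images.

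| Common failure rate | Fisher size | Boschloo size |
|---|---|---|
| 10% | 0.7% | 0.7% |
| 20% | 1.8% | 2.1% |
| 30% | 1.8% | 3.3% |
| 40% | 1.9% | 4.1% |
| 50% | 2.0% | 4.1% |
| Maximum | 2.02% | 4.14% |

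**Other readings of the comparison.** Fisher's maximum is 3.2% for pooled everolimus v control (32 v 16) and 4.1% for a 2 × 3 exact test at 16/16/16.

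**Power, 16 v 16.** The same double sum, with different rates in the two arms. The first three pairs read the plan's 0.9 as a difference on the arcsine scale, 2·asin√p₁ − 2·asin√p₂ = 0.9, which is an assumption. The others are illustrative.

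| Failure rates | Fisher | Boschloo | Gain (points) |
|---|---|---|---|
| 50% v 10.8% | 55.1% | 64.2% | 9.1 |
| 60% v 17.8% | 56.4% | 68.4% | 12.0 |
| 40% v 5.4% | 54.6% | 57.2% | 2.6 |
| 50% v 20% | 28.1% | 39.2% | 11.1 |
| 30% v 10% | 16.8% | 18.4% | 1.6 |

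At 30% v 5% the gain is only 0.8 points (31.1% to 31.9%).

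**Why not the uncorrected chi-square.** Section 10.7 mentions a chi-square test for acute rejection. At 16 v 16 its maximum size is 5.8%, so it does not guarantee the level.

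**How much is timing.** At 50% v 20%, a simulated log-rank test under proportional hazards has 43.9% power, against 39.2% for Boschloo and 28.1% for Fisher. About 11 of the 16 points come from Fisher's conservatism and about 5 from timing. At 30% v 10% the split reverses: log-rank 28.9%, Boschloo 18.4%, Fisher 16.8%.

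**The case against.** Fisher's test is valid and conventional at this size, and a conservative test is not a wrong one. That stands: the change is an improvement, not the correction of an error. The trial is also a pilot with its size set by a rule of thumb, and section 4 calls it non-inferiority without giving a margin, so power to detect a difference may not be its criterion. This too has weight. But the tests named for the composite are difference tests, and for those an exact test that uses more of the level is preferable.

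Three stronger readings are tempting, and the documents do not support them.

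- A reader might infer that the plan throws event dates away. It does not: sections 10.4.4 and 10.5.1 already plan Kaplan-Meier and log-rank analyses of the composite and of each component.
- A reader might take 2% as the size of the planned test in general. It holds only for 16 v 16, and the plan never says that the comparison is pairwise.
- A reader might conclude that log-rank should be the main test because it usually has more power. Its advantage depends on when failures occur. The synopsis objectives and the objectives paragraph closing section 1 count delayed graft function as failure; sections 3.1, 10.4.1 and 10.4.4 do not. If it counts, many failures could share one early time. In a simulation with all failures tied early, a permutation log-rank had 55%, 56% and 52% power for the first three pairs, no better than Fisher (55%, 56%, 55%).

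**Conclusion.** The point holds for pairwise 16 v 16 comparisons: Fisher's true size is at most 2.0% against a nominal 5%, and Boschloo raises the ceiling to 4.1% while still guaranteeing the level. The size bounds are exact and need no assumed rate. The power gain does: about 2 to 12 points for the five tabulated pairs, largest at moderate failure rates and close to nothing when failures are few. For pooled or three-arm comparisons less of the level is unused (maximum 3.2% and 4.1%), and the gain there was not calculated. The ANOVA label in section 10.4.2 means that Fisher cannot be assumed to be the decisive test, so the remedy must settle that as well.

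**What to change.** 1. In the synopsis and section 10.7, replace Fisher's exact test with Boschloo's exact unconditional test for pairwise comparisons of the composite and its components at Month 24. State that the comparisons are pairwise, which pairs are meant, and that Fisher's two-sided p-value is the test statistic.
2. In section 10.4.2, name this test as decisive for the composite in place of the ANOVA.
3. In section 10.4.4, keep Kaplan-Meier and log-rank as supportive, and reword the comparison for three arms.
4. Make these changes before data lock.

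The cost is wording, slightly more computing and a test that readers know less well; no data or patients are added. One consequence should be accepted knowingly: if each everolimus arm is compared with control, the added maximum sizes are 2 × 4.14% = 8.3% with Boschloo, against 2 × 2.02% = 4.0% with Fisher. The plan has no multiplicity rule, so it should say whether each comparison stands alone at 0.05.
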